7.1.2. Multiplicity

Multiplicity is not a concern in this study since no statistical tests are being performed on the efficacy endpoints.

7.2. Primary Endpoint

There are no primary efficacy endpoints in this study.

7.3. Secondary Endpoints

7.3.1. Annualized Bleeding Rate

The ABR will be summarized using categorical (e.g., 0, >0-5, >5-10, >10-20, etc.) and descriptive statistics by treatment regimen in study 9HB01EXT for the FAS for subjects from study 998HB102. For subjects from study 9HB02PED, the summaries will be by age cohort (<6 years old and 6 to <12 years old) from study 9HB02PED and treatment regimen in study 9HB01EXT. All types of bleeding episodes (spontaneous, traumatic, and type unknown) will be included in determining the annualized number.

As a description of the raw data collected in this study, the unadjusted number of bleeding episodes per subject will be summarized using categorical (e.g., 0, 1-3, 4-6, 7-10, 11-15, etc.) and descriptive statistics over all bleeding episodes and by type of bleed (spontaneous, traumatic, and type unknown). The number and percentage of subjects experiencing a bleeding episode will be summarized categorically for any bleeding episode and for each type of bleed by location (joint, muscle, internal, skin/mucosa, and unknown); percentages will be based on the number of subjects in each treatment arm and overall in study 998HB102, each age cohort and overall in study 9HB02PED for the FAS and each treatment regimen in study 9HB01EXT. Of note, the number of subjects with a bleeding episode for which the location is unknown will be tabulated in these summaries but no further analysis of unknown bleeding locations is planned. The total subject years followed will be provided in order to put the unadjusted numbers in perspective.

In addition, summaries of the ABR will also be provided for the following subgroups:

- type of bleed (spontaneous, traumatic)
- location of the bleed (joint, muscle, internal, skin/mucosa)
For the purpose of analysis bleeding episodes with a location of iliopsoas will be treated as a muscle bleed; however, the location will be displayed as iliopsoas in the listings.
- other combinations of type and location of bleed (spontaneous muscle, spontaneous internal, spontaneous skin/mucosa, traumatic joint, traumatic muscle, traumatic internal, traumatic skin/mucosa)
- target joint at screening in the parent study
- contemporaneous entry compliance of $\geq 80\%$, as described in Section 6.5.5.3.

7.3.2. Total Number of Days of Exposure

The total number of exposure days (EDs) along with the duration of dosing to rFIXFc and total number of injections per subject will be summarized. The summary will use the Safety Analysis Set; these data will be summarized by treatment regimen and overall.

In this summary, for any subject, the total number of EDs, duration of dosing to rFIXFc, and total number of injections will be calculated from the start date and time of the starting treatment regimen to the end date and time of the last treatment regimen in study 9HB01EXT. The start and end of treatment regimens are defined in Section 5.3.1. An ED is a 24-hour period in which one or more rFIXFc injections are given. The 24-hour window starts from the first rFIXFc injection on the study and then for subsequent injections, it starts from an injection taken after/outside of a previously identified ED.

The total number of EDs on rFIXFc for each subject will be summarized categorically (i.e., <50 , $50-<100$, $100-<150$, $150-<200$, $200-<250$, etc.) and with descriptive statistics. The total number of injections per subject will be summarized by treatment regimen and overall using descriptive statistics.

Any interruptions to dosing will be ignored for the purposes of calculating the interval. The number and percentage of subjects whose duration of dosing was at least 13 weeks, at least 26 weeks, at least 39 weeks, at least 52 weeks, and at least 78 weeks will be tabulated based on the integer part of the calculated week.

Duration of rFIXFc dosing (weeks) will also be summarized using descriptive statistics. Weeks will be represented in the descriptive statistics as if these were data collected with 1 decimal place.

This table will also be presented by subgroup based upon contemporaneous entry compliance of $\geq 80\%$, as described in Section 6.5.5.3.

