3. SYNOPSIS

This is a brief summary. For details refer to the body of the protocol.

Protocol Number:	9HB01EXT
Protocol Title:	An Open-Label, Multicenter Evaluation of the Long-Term Safety and Efficacy of Recombinant Human Coagulation Factor IX Fusion Protein (rFIXFc) in the Prevention and Treatment of Bleeding Episodes in Previously Treated Subjects With Hemophilia B.
Version Number:	4
Name of Study Treatment:	rFIXFc (BIIB029)
Study Indication:	Hemophilia B
Phase of Development:	3
Rationale for the Study:	To evaluate the long-term safety and efficacy of rFIXFc for the prevention and treatment of bleeding episodes in previously treated subjects with hemophilia B, and to allow subjects from the Phase 3 pivotal study (998HB102), the pediatric study (9HB02PED), or any other rFIXFc study (parent studies) to continue treatment with rFIXFc.
Study Objectives and Endpoints:	Objectives Primary: The primary objective of the study is to evaluate the long-term safety of rFIXFc in subjects with hemophilia B. Secondary: The secondary objective of this study is to evaluate the efficacy of rFIXFc in the prevention and treatment of bleeding episodes in subjects with hemophilia B. Endpoints Primary: The occurrence of inhibitor development. Secondary: 
• The annualized number of bleeding episodes per subject• The annualized number of spontaneous joint bleeding episodes per subject• The total number of days of exposure per subject per

CONFIDENTIAL

The information contained herein may not be used, disclosed, or published without the written consent of Biogen Idec MA Inc.

year

- The consumption of rFIXFc as total dose per kg per subject per year
- Physician's global assessment of the subject's response to his treatment regimen using a 4-point scale
- Subject's/caregiver's assessment of response to the treatment of bleeding episodes using a 4-point scale

Endpoints for Major Surgeries:

- Investigator/Surgeon assessment of hemostatic response to surgery using the 4-point bleeding response scale
- Number of injections and dose per injection to maintain hemostasis during the surgical period
- Estimated blood loss (mL) during surgery and the post-operative period
- Number of blood product units transfused during surgery

Patient-Reported and Health Outcome Endpoints:

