6.2.2. Secondary Endpoints

The secondary endpoints are as follows:

- The annualized number of bleeding episodes per subject
- The annualized number of spontaneous joint bleeding episodes per subject
- The total number of days of exposure per subject per year
- The consumption of rFIXFc as total dose per kg per subject per year
- Physician's global assessment of the subject's response to his treatment regimen using a 4-point scale
- Subject's/caregiver's assessment of response to the treatment of bleeding episodes using a 4-point scale

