16.6.2. Methods of Analysis

For the analysis of safety, data in 9HB01EXT will be integrated with the parent study data, unless specified otherwise. The incidence of AEs will be tabulated overall, by severity, and by relationship to treatment. In addition, the incidence of AEs will be presented by exposure day (ED) intervals. An ED is a 24-hour period, in which one or more rFIXFc injections are given.

CONFIDENTIAL

The information contained herein may not be used, disclosed, or published without the written consent of Biogen Idec MA Inc.

Subject listings will be provided for all AEs, SAEs, AEs resulting in discontinuation of the study treatment or withdrawal from the study, and death. Findings for clinical lab values will be summarized by descriptive statistics. Listings of vital signs and abnormal laboratory test results will be provided.

The total number of EDs of rFIXFc will be summarized by treatment regimen and overall for 9HB01EXT, and overall using combined data from the parent studies and 9HB01EXT.

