11. INDEPENDENT DATA SAFETY MONITORING COMMITTEE

There will be no independent data safety monitoring committee for this study.

LIST OF TABLES, LISTINGS, AND FIGURES

List of Tables (Table titles are suggested. If appropriate, table titles may change during their creation.)

Summary of disposition

Subjects from study 998HB102:

Summary of enrollment by country and site

Summary of subjects attending each visit

Summary of demographic and baseline characteristics

Summary of medical and surgical history

Summary of concomitant medications

Summary of major protocol deviations

Summary of major protocol deviations based on EPD data in the original pre-change state

Summary of exposure

Summary of exposure by EPD entry compliance

Summary of last prescribed dose and dosing frequency

Summary of changes in study 9HB01EXT treatment regimens

Summary of prophylactic dose (IU/kg)

Summary of prophylactic dosing interval

Summary of annualized rFIXFc consumption (IU/kg)

Summary of bleeding episodes

Summary of annualized bleeding rate

Summary of annualized bleeding rate by type of bleeds

Summary of annualized bleeding rate by location and type of bleeds

Summary of annualized bleeding rate by the presence of target joints at screening in parent study

Summary of annualized bleeding rate by EPD entry compliance

Summary of subject's assessment of response to rFIXFc injections for the treatment of bleeding episodes

Summary of number of injections required for resolution of a bleeding episode

Summary of dose (IU/kg) of rFIXFc for resolution of bleeds

Summary of number of days from the last prophylaxis injection to a spontaneous bleeding episode

Summary of time (hours) between first and second injection to treat a bleeding episode

Summary of time (hours) between first and second injection to treat a bleeding episode by type of bleed

Summary of results and change from study 9HB01EXT baseline: HAEMO-QoL total score and sub-score (Children and Teenagers aged 13-16)

Summary of results and change from study 9HB01XT baseline: HAEM-A-QoL total score and sub-score (Adults)

Summary of EQ-5D-L descriptive system

Summary of results: EQ-5D-L visual analogue scale

Summary of hemophilia-related health economic parameters

Summary of health economic parameters for all physician and emergency room visits

Summary of results and changes from study 9HB01EXT baseline: Modified Hemophilia Joint Health Score (HJHS)

Subjects from study 9HB02PED:

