Listing of subjects with large gap between the parent study and study 9HB01EXT
Listing of subject disposition

Listing of major and minor protocol deviations
Listing of major and minor protocol deviations based on EPD data in the original pre-change state
Listing of demographic and baseline characteristics
Listing of medical and surgical history
Listing of prior and concomitant medications
Listing of medications taken after the End of Study Visit
Listing of other therapy or concomitant procedures
Listing of prescribed dose and dosing regimen changes
Listing of the Investigator's classification of bleeding episodes which differed from the subject's/caregiver's classification
Listing of weight
Listing of all injections and treated bleeding episodes
Listing of derived bleeding endpoints based on individual bleeding episodes
Listing of derived bleeding and injection endpoints based on subjects
Listing of compliance and exposure
Listing of exposure
Listing of injections to treat a bleed
Listing of the by-subject summary of the assessment of response to rFIXFc for the treatment of bleeding episodes
Listing of dose and consumption endpoints
Listing of the number of bleeding episodes during the efficacy period
Listing of physician's assessment of the subject's global response to his treatment regimen
Listing of major surgery information – hospitalization data
Listing of major surgery information – blood loss
Listing of major surgery information – dosing during and for the first 14 days post-surgery
Listing of major surgery information – transfusions and surgeon's assessment of hemostatic response to rFIXFc
Listing of minor surgery information – hospitalization data
Listing of minor surgery information – blood loss
Listing of minor surgery information – dosing during and on the day of surgery
Listing of minor surgery information – transfusions and surgeon's assessment of hemostatic response to rFIXFc
Listing of injections and bleeding episodes during and for the first 14 days following major surgery
Listing of FIX activity levels
Listing of adverse events
Listing of adverse events reported during major surgical/rehabilitation periods
Listing of serious adverse events
Listing of adverse events leading to discontinuation of treatment and/or the study
Listing of adverse events reported in study 9HB01EXT that started before 9HB01EXT Study Day 1 but were not reported in the parent study
Listing of deaths
Listing of laboratory normal ranges

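### The secondary endpoint of exposure days per subject per year has no per-year derivation in SAP 7.3.2, which summarizes totals only

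*SAP*

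**What the plan says.** The endpoint is a rate. Protocol 6.2.2 lists "The total number of days of exposure per subject per year", and SAP 2.2.2 repeats it among the secondary efficacy endpoints. The synopsis has the same item, "The total number of days of exposure per subject per", with the word year falling after a page break.

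SAP 7.3.2 sits under Secondary Endpoints, and SAP 6.5.1.1 defers to it. Its heading drops the time unit. EDs, injections and dosing duration are each "calculated from the start date and time of the starting treatment regimen to the end date and time of the last treatment regimen". Then "The total number of EDs on rFIXFc for each subject will be summarized categorically", in bands of 50, and with descriptive statistics. Duration gets weekly cut-points, and "Duration of rFIXFc dosing (weeks) will also be summarized using descriptive statistics". No sentence relates EDs to duration.

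The planned outputs are a summary of exposure, "Summary of exposure by EPD entry compliance", and listings such as "Listing of compliance and exposure". No title mentions an annualized ED figure.

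The two neighbouring endpoints are treated differently. SAP 7.1.1 (bleeding rate) and SAP 6.5.4 (consumption) each divide by days in the efficacy period and multiply by 365.25.

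**The concern.** If the SAP is followed as written, a named secondary endpoint is replaced by a different quantity. That would matter little if everyone stayed equally long on one regimen, but they do not. Under SAP 3.1 a stay may run to 4 years or stop when the product reaches the local market. Under SAP 5.3.1 a subject who switches counts in each regimen for the time spent there. A by-regimen table of total EDs therefore reflects how long people stayed as well as how often they were dosed.

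The SAP already accepts this reasoning for bleeds. In 7.3.1 it supplies total subject-years so that raw bleed counts can be read in context. For EDs, the raw count is the only ED measure planned.

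**Working it through.** The documents state no annualized ED figure, so there is nothing to reproduce. The check asks whether a total can stand in for the rate, and what a rate would still need specified.

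**Inputs.** Weekly prophylaxis is every 7 days and individualized prophylaxis every 8 to 16 days (SAP 3.2.1.2). The annualizing form is count / days x 365.25 (SAP 6.5.4 and 7.1.1). Assumptions: one ED per scheduled dose, and no bleed or surgery doses except where stated.

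**Same total, different rates.**
- Every 8 days for 1 year: 365.25 / 8 = 45.66 EDs, or 45.7 per year.
- Every 16 days for 2 years: 730.5 / 16 = 45.66 EDs, or 22.8 per year.

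**Same rate, different totals.** Weekly dosing with the window opening just after a dose gives 365.25 / 7 = 52.2 per year. The total and its 7.3.2 band depend on stay:

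| Stay | Total EDs | Band |
|---|---|---|
| 6 months | 26.1 | under 50 |
| 1 year | 52.2 | 50 to under 100 |
| 2 years | 104.4 | 100 to under 150 |
| 4 years | 208.7 | 200 to under 250 |

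**Dividing the published means does not recover the endpoint.** Take the first two subjects above. Mean EDs over mean duration is 45.66 / 1.5 = 30.4 per year. The mean of their rates is (45.66 + 22.83) / 2 = 34.2.

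**The window matters.** SAP 7.3.2 runs from the start of the first regimen to the end of the last and ignores interruptions. The efficacy period (SAP 5.3.2) removes surgical periods and, in prophylaxis, injection gaps over 42 days. For an assumed weekly subject over one year, the efficacy-period rate is 52.2. The regimen-duration rate is as follows.
- One 28-day surgical period holding 7, 14 or 28 EDs: (365.25 - 28) / 7 = 48.18, plus 7, 14 or 28, gives 55.2, 62.2 or 76.2 (+6%, +19%, +46%).
- One gap of 43, 60 or 90 days instead: (365.25 - gap) / 7 gives 46.0, 43.6 or 39.3 (-12%, -16%, -25%).

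**Short durations matter.** Under SAP 5.3.1, a prophylaxis subject entering after a long gap starts at the first dose. A new prophylactic regimen also starts at its first dose. A last prophylactic regimen ends at its last dose. Where both apply, n doses at interval d span (n - 1) x d days, so the rate is (365.25 / d) x n / (n - 1). For weekly dosing:
- n = 2: 2 / 7 x 365.25 = 104.4
- n = 4: 4 / 21 x 365.25 = 69.6
- n = 27: 27 / 182 x 365.25 = 54.2
- n = 1: zero days, so the rate is undefined.

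**The case against.** The best reply is that little information is lost. Total EDs, injections and duration stand in one summary, with descriptive statistics. Average prophylactic dosing interval (SAP 6.5.3) and annualized consumption are also tabulated. Subject-level exposure listings are planned. The primary endpoint is inhibitor development, and no hypothesis is tested. All of that is correct and limits the weight of the point. It does not remove it: the interval covers only prophylactic dosing (including additional injections in the personalized regimen) over stretches not separated by a bleed, consumption is in IU/kg, and the listings leave the reader to build the summary. The table shells are not in the documents and the table titles are described as suggestions, so the gap is shown for the SAP text and not for every eventual output.

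Three stronger readings are tempting, and the documents do not support them.
- Protocol 16.6.2 also plans totals ("The total number of EDs of rFIXFc will be summarized by treatment regimen and overall for 9HB01EXT"), and a reader might call that a second failure. It is a safety-exposure method, and cumulative EDs are apt there because the inhibitor denominators in protocol 16.7.2 use 50 and 100 EDs.
- A reader might infer that the exposure results will be biased. The examples show only that a total does not identify a rate.
- A reader might say that the documents dictate the window. Listing the endpoint with the efficacy endpoints points to the efficacy period; 7.3.2 as written points to regimen duration. Neither is prescribed for a rate.

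**Conclusion.** The point holds. The endpoint is defined per year in both documents, and the implementing section gives a total. This is a mismatch with the endpoint definition, more than missing detail, and should be corrected before the final analysis. It affects how one secondary endpoint is described. It affects no test, no error rate and not the primary endpoint.

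The size in the actual data cannot be stated. The illustrations rest on idealized dosing: equal totals can hide a twofold difference in rate (45.7 against 22.8 per year), and the choice of window moved the assumed one-year examples by -25% to +46%. Annualizing alone is not sufficient, because a first-dose-to-last-dose window inflates short stays.

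A separate minor point concerns bleed type. Protocol 7.1.4.1 uses the Investigator's spontaneous or traumatic classification whenever it differs from the diary. SAP 7.1.1 applies it where the subject or caregiver agreed. A reader might infer that the diary prevails on disagreement, but the SAP is silent on that case. A listing of differing classifications is planned, the number of disputed bleeds is not given and may be zero, and the overall bleeding rate is unaffected.

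**What to change.** In SAP 7.3.2, add for each subject, by regimen and overall: annualized EDs = EDs / days x 365.25, with numerator and denominator from the same window. Report this as the endpoint and keep total EDs, injections and duration as the exposure table.

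The sponsor should choose and state the window. The efficacy period (5.3.2) matches the bleeding rate and consumption. The regimen duration (5.3.1) matches the present 7.3.2 count.

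State how zero and very short durations are handled. Name long-gap entrants and switchers whose last regimen starts and ends on a dose. Possible rules are to leave the opening dose out of the numerator when the window opens on it, or to set a minimum duration for the rate. Either way, a subject with no rate stays in the totals. The efficacy period's requirement of at least 2 prophylactic injections helps with zero durations but not with short ones. It is worded for the study as a whole, so its effect on a single-dose regimen should be spelled out.

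Separately, reconcile the bleed-type rule in SAP 7.1.1 with protocol 7.1.4.1.

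Cost: a paragraph of SAP text, one derived variable, one row in the exposure tables and one sentence in 7.1.1. All data are already collected.

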7.3.3. Total Annualized rFIXFc Consumption

The secondary endpoint of total annualized rFIXFc consumption per subject for the prevention and treatment of bleeding episodes will be summarized by treatment regimen in study 9HB01EXT for the FAS for subjects from study 998HB102. For subjects from study 9HB02PED, the summaries will be by age cohort (<6 years old and 6 to <12 years old) from

study 9HB02PED and by treatment regimen in study 9HB01EXT. See Section 6.5.4 for details on the annualized rFIXFc consumption derivation.

7.3.4. Physician's Global Assessment of the Subject's Response to His rFIXFc Regimen

Investigators will record assessments of each subject's response to his rFIXFc regimen at each scheduled visit using the following 4-point scale:

- 1=Excellent: bleeding episodes responded to \leq the usual number of injections or \leq the usual dose of rFIXFc, or the rate of breakthrough bleeding during prophylaxis was \leq that usually observed.
- 2=Effective: most bleeding episodes responded to the same number of injections and dose, but some required more injections or higher doses, or there was a minor increase in the rate of breakthrough.
- 3=Partially Effective: bleeding episodes most often required more injections and/or higher doses than expected, or adequate breakthrough bleeding prevention during prophylaxis required more frequent injections and/or higher doses.
- 4=Ineffective: routine failure to control hemostasis or hemostatic control requires additional agents.

Investigators should consider the following, if available, when making the assessment:

- Frequency of rFIXFc injections
- Response to rFIXFc injection
- Information reported in the eDiary by the subject

The physician's global assessment of the subject's response will be summarized by visit for overall treatment regimen for the FAS. The number and percentage of subjects in each response category will be tabulated. Percentages will be based on the number of subjects for whom an assessment was provided at the respective visit. This table will also include a cumulative tabulation across all scheduled study visits; subjects can be included in this tabulation up to all visits, once for each visit. Percentages for this collection of responses throughout the study will be based on the total number of assessments across all visits. Assessments taken during major surgical/rehabilitation periods will not be included in the summary but will be included in the listings and flagged.

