If the study is stopped, the events will be investigated, enrollment will be stopped, and current subjects will stop dosing with rFIXFc. If, in consultation with the Sponsor's Safety Surveillance Team, it is determined that the study should be permanently discontinued, then subjects will attend a final visit.

CONFIDENTIAL

The information contained herein may not be used, disclosed, or published without the written consent of Biogen Idec MA Inc.

Tests and Assessments¹	Visit 1 ²	Visit 2 Month 6 (±2 weeks)	Visit 3 Month 12 (±2 weeks)	Visit 4 Month 18 (±2 weeks)	Visit 5 Month 24 (±2 weeks)	Visit 6 Month 30 (±2 weeks)	Visit 7 Month 36 (±2 weeks)	Visits Semi- Annually (Every 6 months) (±2 weeks)
to Individual Bleeding Episodes Treated in Clinic								
Physician's Global Assessment of Response to the Treatment Regimen	X	X	X	X	X	X	X	X
HJHS ^{1,4}	X		X		X		X	X
AE/SAE Monitoring and Recording	X	Monitor and record at all visits; telephone call every 2 months for AE/SAE assessments						
Concomitant Therapy/Procedures Recording	X	Monitor and record at all visits; telephone call every 2 months						

AE=adverse events; HJHS=Hemophilia Joint Health Score; QoL=quality of life; SAE=serious adverse events

Table footnotes are presented on page 24.

CONFIDENTIAL

The information contained herein may not be used, disclosed, or published without the written consent of Biogen Idec MA Inc.

Footnotes for Screening and Treatment Period

1. Subjects who enroll into 9HB01EXT will be assessed only for those parameters at had been previously assessed in the parent study.

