2. The End of Treatment (EOT) visit for the parent study may serve as the Screening Visit for the extension study. Written informed consent and subject assent, if applicable, for participation in the extension study must be obtained at this visit before any extension study-related procedures are conducted. The subject or his Parents/legal guardians should receive the informed consent information prior to this visit to allow adequate time for review at home, and discussion with the Investigator. Data on medical history, demographics, screening tests, ongoing adverse events and concomitant therapy, and EOT tests and assessments will be transferred from the parent rFIXFc study, so it will not be necessary to repeat these assessments at Visit 1. An HJHS or modified HJHS assessment, as appropriate, should be performed at Visit 1 in ALL subjects. Study eligibility must be verified prior to study enrollment. Subjects who enroll with a gap of greater than 37 days following the EOT Visit for the previous study should have all laboratory assessments performed and reviewed by the Investigator at Visit 1, prior to dosing with rFIXFc, to assess safety and inclusion/exclusion parameters. The time allotted for Visit 1 may span a sufficient interval to allow for laboratory results to be reviewed and confirmed as suitable by the Investigator. Otherwise, more than 1 clinic visit may be required prior to dosing with rFIXFc.
3. Medical and surgical history includes any significant medical condition and/or any significant surgical histories that occurred prior to the subject enrollment in the parent study.
4. Physical examination will include assessments of the skin, head, eyes, ears, nose, throat (HEENT), lymph, neck, chest/lungs, heart, vascular system, abdomen, musculoskeletal and neurological function, extremities, and joints. Following Visit 7, physical examination will be performed on an annual basis.
5. Vital signs assessments include blood pressure, pulse rate, respiratory rate and temperature (°C), and should be taken after the subject has been resting supine for 5 minutes. At dosing visits, vital signs should be measured pre-injection and post-injection.

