1. INTRODUCTION

Hemophilia B, or Christmas disease, is a deficiency in the clotting Factor IX (FIX) and is an X-chromosome linked inherited coagulation disorder, affecting approximately 80,000 people worldwide [Giangrande, 2005; World Federation of Hemophilia (WFH), 2005]. The deficiency of FIX results in bleeding into joints, soft tissue, and muscle that can be associated with trauma or can occur in the absence of trauma (spontaneous bleeding). Depending on the severity of the bleeding it can also pose a life-threatening situation (e.g. intracranial hemorrhage, other internal bleeding) for a subject if not treated appropriately.

There is no available cure for hemophilia B, so treatment focuses on the replacement of FIX with the intravenous (IV) administration of FIX-containing coagulation products. The goal of treatment with FIX-containing coagulation products is to raise the circulating level of FIX to achieve either resolution of bleeding (on-demand treatment) or prevention of bleeding (prophylaxis treatment) [Roberts, 1993; WFH, 2005; MASAC, March 2009]. The frequency of administration of FIX products differs among subjects and is usually tailored to the subject's clinical status, taking into consideration the type of bleeding episode, frequency of bleeding, and goal of treatment for the subject. The dose of FIX required also varies and has been based on observations over the years and guidelines established by organizations such as the National Hemophilia Foundation of the United States and the WFH [Roberts, 1993; WFH 2005]

This statistical analysis plan is for the purpose of providing an analysis of long term safety and efficacy data on rFIXFc to support the generation of long-term data on safety, efficacy and other patient reported outcomes. The analysis is based on study 9HB01EXT data only. Study subjects refer only to those subjects enrolled into this study from parent studies 998HB102 and 9HB02PED. A parent study is defined as a study where subjects may be enrolled into 9HB01EXT after study completion.

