7.5.6. Health-Economic Parameters

Health-economic assessments consist of the following items based on the time period since the last visit at which they were assessed:

- Number of hospitalizations excluding planned hospitalizations, elective surgery documented at Visit 1, and emergent surgery
- Number of emergency room visits
- Number of physician visits, excluding study visits
- Number of hospitalization days
- Number of days off work, school, day care, or preschool
- Number of days off work for the parent or caregiver

The previous visit for the Visit 1 refers to the previous visit in the parent study where applicable.

These data will be tabulated categorically at each visit for overall treatment regimen for the FAS. Information collected on the questionnaire relates to both hemophilia and non-hemophilia related events. Thus, in addition to summarizing the hemophilia-related health resource utilization, the utilization for hemophilia- and non-hemophilia related events will be combined and the total summarized for the last 4 assessments listed above.

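### The cumulative Physician's Global Assessment row in SAP 7.3.4 includes the Visit 1 rating, which reflects the parent-study period; limit the row to visits after Visit 1

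*SAP*

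**What the plan says.** The Physician's Global Assessment is one of six secondary endpoints (Protocol 6.2.2, SAP 2.2.2). Under SAP 7.3.4, "Investigators will record assessments of each subject's response to his rFIXFc regimen at each scheduled visit", on a four-point scale. The table first gives counts and percentages for each visit, all regimens together. Then: "This table will also include a cumulative tabulation across all scheduled study visits". A subject may enter that row once per visit, and its percentages "will be based on the total number of assessments across all visits". One exclusion is stated: "Assessments taken during major surgical/rehabilitation periods will not be included in the summary".

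On Visit 1:

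- The schedule in Protocol Section 4, Table 1 marks the "Global Assessment of Response to the Treatment Regimen" in every column, starting with Visit 1.
- Footnote 2 to that table allows the parent study's End of Treatment (EOT) visit to serve as the screening visit and says that "EOT tests and assessments will be transferred from the parent rFIXFc study, so it will not be necessary to repeat these assessments at Visit 1".
- SAP 5.1.2 treats Visit 1 as a scheduled extension visit, says the parent EOT visit will serve as the baseline visit, and allows baseline assessments to have been repeated after a gap in treatment.
- SAP 5.1.3 defines post-baseline as anything after 9HB01EXT Visit 1.

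On scope, SAP 1 states: "The analysis is based on study 9HB01EXT data only". For the health-economic items, SAP 7.5.6 recognises that Visit 1 looks backwards: "The previous visit for the Visit 1 refers to the previous visit in the parent study where applicable". SAP 7.3.4 has no comparable remark.

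**The concern.** The rating is retrospective. The investigator judges how bleeds responded to injections, how often breakthrough bleeding occurred, and what the diary shows. At Visit 1 that history belongs to the parent study. SAP 5.1.2 makes Visit 1 the baseline, yet SAP 7.3.4 lets the same visit contribute an outcome to the pooled row.

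At stake is the one figure that summarises this secondary endpoint over the whole extension. If it mixes in parent-study ratings, it does not measure what its label says. The mixing is also uneven: subjects who leave early contribute proportionally the most from Visit 1.

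**Working it through.** The plan states no figure for this row, and all analyses are descriptive, so there is nothing to reproduce. The check traces the text and then sizes the effect.

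**Is Visit 1 in the row?** SAP 7.3.4 covers every scheduled visit. Protocol Table 1 schedules the rating at Visit 1, and SAP 5.1.2 calls Visit 1 scheduled. The single exclusion does not concern Visit 1 as such. So the row as written includes it.

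**What does the Visit 1 rating describe?**

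- If it is the transferred EOT rating, it describes the parent study.
- If it is newly made after a short gap, SAP 5.1.1 places Study Day 1 at the last day of the parent study. Extension time before Visit 1 is then at most 14 days (from 998HB102) or 7 days (from 9HB02PED).
- If the gap exceeds 37 days, footnote 2 calls for laboratory assessments at Visit 1 before dosing. A new rating made at that point would precede extension dosing.

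In each case the rating looks back essentially on the parent-study period.

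**Size.** Inputs: visits every 6 months after Visit 1 (Protocol 7.1); follow-up of up to 4 years (Protocol 7.2); about 120 subjects, 100 + 20 (Protocol 16.10). Assume every visit is attended and rated.

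With k visits after Visit 1:

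- Visit 1 share of a subject's pooled ratings = 1/(k+1).
- Shift in the pooled percentage = (Visit 1 percentage − later percentage)/(k+1).

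The last column assumes a 10-point difference between Visit 1 and later ratings; the documents give no ratings.

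| Follow-up | k | Visit 1 share | Shift per assumed 10 points |
|---|---|---|---|
| 6 months | 1 | 1/2 = 50.0% | 5.0 |
| 12 months | 2 | 1/3 = 33.3% | 3.3 |
| 24 months | 4 | 1/5 = 20.0% | 2.0 |
| 36 months | 6 | 1/7 = 14.3% | 1.4 |
| 48 months | 8 | 1/9 = 11.1% | 1.1 |

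An assumed 20-point difference doubles the last column (6.7 points at 12 months, 2.2 at 48).

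For a table with mixed follow-up, n subjects each give one Visit 1 rating and k_i later ones. The Visit 1 share is n/(n + Σk_i) = 1/(1 + mean k), so the same column applies with k read as the mean number of later visits.

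For 120 subjects all followed to Month 36, the row holds 120 × 7 = 840 ratings, of which 120 come from Visit 1. Removing those leaves 720.

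**The case against.** Several points count on the other side.

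- *SAP 7.3.4 does not name Visit 1.* On the extension-data-only rule of SAP 1, a programmer might drop a transferred rating. That is possible, but it would mean overriding the explicit all-visits wording with a general statement. The text needs settling either way.
- *A reader might infer that the Visit 1 rating always is the parent-study EOT rating.* The documents do not support that. The protocol says only that the EOT visit may serve as screening, and SAP 5.1.2 allows repeats after a gap. What stands is weaker but sufficient: a new rating at Visit 1 would look back on much the same period.
- *The by-visit rows already show Visit 1.* This is correct. Anyone can subtract the Visit 1 counts from the cumulative counts to obtain the post-baseline figure exactly. No information is lost; the problem is confined to the pooled row.
- *Protocol 16.4.2 has visit-based efficacy endpoints use all study visits, even outside the efficacy period, except those coinciding with major surgical or rehabilitation periods.* SAP 7.3.4 follows that rule. But the rule concerns visits outside the efficacy period; it does not turn a rating of the time before the extension into an extension outcome. The protocol also planned to integrate parent-study data (Section 16), whereas the SAP limits itself to extension data. The fix does narrow the protocol wording, and the SAP should say so.
- *The endpoint is descriptive.* This is also correct: no test, error rate or decision rule depends on the row.

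**Conclusion.** The point holds for one row of one table. As written, the cumulative tabulation pools a rating of essentially parent-study response with ratings of extension response. With full attendance, Visit 1 makes up between a third (12 months) and a ninth (48 months) of the pooled ratings, and half for a subject with only the Month 6 visit after Visit 1.

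A reader might infer that the pooled figure is inflated, because subjects who finished a parent study and chose to continue may have been rated favourably at its end. The documents contain no ratings, so neither the direction nor the size of any distortion is established. The 10-point difference is a scale for judging sensitivity, not an estimate.

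Nor should the point be read as undermining the endpoint as a whole or the other analyses. The by-visit percentages are unaffected, as are the primary endpoint, the annualized bleeding rate and consumption. It is a worthwhile correction to a named secondary endpoint's summary, and it should be made before the table is programmed.

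**What to change.** In SAP 7.3.4:

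1. Limit the cumulative tabulation, numerator and denominator, to post-baseline scheduled visits, meaning those after 9HB01EXT Visit 1 as defined in SAP 5.1.3. Keep the existing exclusion for major surgical and rehabilitation periods.
2. Keep the Visit 1 row in the by-visit part and label it as baseline, reflecting parent-study response.
3. State that this narrows the all-visits wording of Protocol 16.4.2 for this row, and why.

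The cost is a short addition to the SAP text, one filter in the table program and a row label. The denominator becomes smaller (720 instead of 840 in the Month 36 example), and the pooled figure may change, possibly to a slightly less favourable value. No data are lost, since Visit 1 remains visible in its own row.
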